Skeletal abnormalities of osteomalacia (rickets) often manifest in the first 2 years of childhood (e.g., bowed legs) when lower extremity bowing becomes evident with the onset of weight bearing; however, the disorder may go undiagnosed until adulthood. The initial presenting complaint in adults may be enthesopathy (calcification of the tendons, ligaments, and joint capsules) (Ruppe 2012). There is a great deal of variability in the manifestations of XLH. In the mildest cases, only hypophosphatemia is evident (Holm et al. 2012). In more severe cases, adult patients with XLH may suffer from bone pain and osteomalacia; increased risk of bone fractures; joint abnormalities and joint pain; osteoarthritis, and enthesopathy (Ruppe 2012); (Tenenhouse et al. 2001); (Reid et al. 1989). Diagnostic testing characteristically reveals low serum phosphate concentration and reduced tubular resorption of phosphate corrected for glomerular filtration rate (TmP/GFR). Additionally in adults, the normal physiologic response to hypophosphatemia of an elevation of 1,25(OH)₂D is absent; serum calcium and alkaline phosphatase (ALP) are within the normal range; and parathyroid hormone (PTH) is normal to slightly elevated. (Ruppe 2012) For definitive evidence of renal phosphate wasting, a 2-hour fasting urine specimen as well as a blood sample collected at the

midpoint of the urine collection period are used to calculate the percent tubular reabsorption of phosphate (TRP) and to determine the tubular threshold maximum for phosphate (Carpenter et al. 2011).

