In conclusion, KRN23 inhibits the effects of FGF23, restoring phosphate, vitamin D and bone metabolism homeostasis. By positively modulating serum phosphorus, it is expected that the underlying osteomalacia will be treated, leading to improved clinical outcomes including a potential reduction in pain, stiffness, and fracture risk as well as the impact of these factors on the quality of life of adult patients with XLH. To date, KRN23 has a favorable safety profile without evidence of increased ectopic mineralization or other concerns associated with the excess of FGF23. KRN23 has the potential to be an effective and safe treatment option for patients with XLH.

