7.5.4 Appropriateness of Measurements

As described in Section 5, XLH is characterized by renal phosphate wasting leading to hypophosphatemia and low or normal concentrations of 1,25(OH)₂D, leading to signs/symptoms of bone pain and osteomalacia; increased risk of bone fractures; joint abnormalities and joint pain; enthesopathy; and osteoarthritis (Tenenhouse et al. 2001); (Reid et al. 1989). Measurements chosen for this study are therefore appropriate to assess the PD impact and safety profile of KRN23 on the disease characteristics over time, as well as to explore the efficacy of KRN23 in improving bone mineralization; strength, balance, and agility; and overall QoL.

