## 5.7 Events To Monitor

**Injection Site Reaction (ISR):** Defined by preferred terms under the Medical Dictionary for Regulatory Activities (MedDRA) high-level term (HLT) “Injection site reaction”.

**Immunogenicity AE:** Defined using relevant PTs in the narrow SMQs for “Hypersensitivity”.

**Hyperphosphataemia AE:** Defined by using PTs: “Hyperphosphataemia”, “Blood phosphorus increased”.

**Ectopic calcification related AE:** There is no available SMQ. Ectopic calcification related AE is defined using a MedDRA search of ‘calcification’.

**Gastrointestinal AEs:** i.e. nausea, vomiting, abdominal pain, diarrhea. Defined using PTs in the narrow SMQ “Gastrointestinal nonspecific inflammation and dysfunctional conditions”.

**Restless leg syndrome AE:** Defined by PTs “Restless legs syndrome”, “Restlessness”, “Akathisia”, “Sensory disturbance”, “Psychomotor hyperactivity”, “Limb discomfort”, “Neuromuscular pain”, “Formication”.

See search criteria in [Appendix 5](#).

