Hypersensitivity	Solvent sensitivity
Hypersensitivity	Stevens-Johnson syndrome
Hypersensitivity	Stoma site hypersensitivity
Hypersensitivity	Stoma site rash
Hypersensitivity	Swelling face
Hypersensitivity	Swollen tongue
Hypersensitivity	Tongue oedema
Hypersensitivity	Toxic epidermal necrolysis
Hypersensitivity	Toxic skin eruption
Hypersensitivity	Tracheal oedema
Hypersensitivity	Type I hypersensitivity
Hypersensitivity	Type II hypersensitivity
Hypersensitivity	Type III immune complex mediated reaction
Hypersensitivity	Type IV hypersensitivity reaction
Hypersensitivity	Urticaria
Hypersensitivity	Urticaria cholinergic
Hypersensitivity	Urticaria chronic
Hypersensitivity	Urticaria contact
Hypersensitivity	Urticaria papular
Hypersensitivity	Urticaria physical
Hypersensitivity	Urticaria pigmentosa
Hypersensitivity	Urticaria vesiculosa
Hypersensitivity	Vaginal exfoliation
Hypersensitivity	Vaginal ulceration
Hypersensitivity	Vasculitic rash
Hypersensitivity	Vessel puncture site rash
Hypersensitivity	Vulval ulceration
Hypersensitivity	Vulvovaginal rash
Hypersensitivity	Vulvovaginal ulceration

Hyperphosphataemia: based on selected PTs below

Category	PT
Hyperphosphataemia	Hyperphosphataemia
Hyperphosphataemia	Blood phosphorus increased

Ectopic mineralization: based on a MedDRA search of 'calcification'

Category	PT
Ectopic calcification	Adrenal calcification
Ectopic calcification	Aortic calcification
Ectopic calcification	Aortic valve calcification
Ectopic calcification	Aortic valve sclerosis
Ectopic calcification	Articular calcification
Ectopic calcification	Bladder wall calcification
Ectopic calcification	Breast calcifications
Ectopic calcification	Bursa calcification
Ectopic calcification	Calcific deposits removal
Ectopic calcification	Calcification metastatic
Ectopic calcification	Calcification of muscle
Ectopic calcification	Calcinosis
Ectopic calcification	Calculus bladder
Ectopic calcification	Calculus prostatic
Ectopic calcification	Calculus ureteric
Ectopic calcification	Calculus urethral
Ectopic calcification	Calculus urinary
Ectopic calcification	Cardiac valve sclerosis
Ectopic calcification	Cerebral calcification
Ectopic calcification	Chondrocalcinosis
Ectopic calcification	Chondrocalcinosis pyrophosphate
Ectopic calcification	Cutaneous calcification
Ectopic calcification	Dystrophic calcification
Ectopic calcification	Heart valve calcification
Ectopic calcification	Heart valve stenosis
Ectopic calcification	Hepatic calcification

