Ectopic calcification	Intervertebral disc calcification
Ectopic calcification	Intestinal calcification
Ectopic calcification	Ligament calcification
Ectopic calcification	Lymph node calcification
Ectopic calcification	Mitral valve calcification
Ectopic calcification	Mitral valve sclerosis
Ectopic calcification	Myocardial calcification

Category	PT
Ectopic calcification	Nephrocalcinosis
Ectopic calcification	Nephrolithiasis
Ectopic calcification	Ovarian calcification
Ectopic calcification	Pancreatic calcification
Ectopic calcification	Pericardial calcification
Ectopic calcification	Pleural calcification
Ectopic calcification	Prostatic calcification
Ectopic calcification	Pulmonary calcification
Ectopic calcification	Pulmonary valve calcification
Ectopic calcification	Pulmonary valve sclerosis
Ectopic calcification	Splenic calcification
Ectopic calcification	Stag horn calculus
Ectopic calcification	Tendon calcification
Ectopic calcification	Tracheal calcification
Ectopic calcification	Tricuspid valve calcification
Ectopic calcification	Tricuspid valve sclerosis
Ectopic calcification	Vascular calcification

Gastrointestinal: based on narrow SMQ “Gastrointestinal nonspecific inflammation and dysfunctional conditions”

Category	PT
Gastrointestinal	Acid peptic disease
Gastrointestinal	Duodenogastric reflux
Gastrointestinal	Dyspepsia
Gastrointestinal	Gastrooesophageal reflux disease
Gastrointestinal	Gastrooesophageal sphincter insufficiency
Gastrointestinal	Chronic gastritis
Gastrointestinal	Colitis
Gastrointestinal	Duodenitis
Gastrointestinal	Enteritis
Gastrointestinal	Erosive duodenitis
Gastrointestinal	Erosive oesophagitis
Gastrointestinal	Feline oesophagus
Gastrointestinal	Functional gastrointestinal disorder
Gastrointestinal	Gastric mucosa erythema
Gastrointestinal	Gastritis
Gastrointestinal	Gastritis erosive
Gastrointestinal	Gastroduodenitis
Gastrointestinal	Gastrointestinal erosion
Gastrointestinal	Gastrointestinal mucosa hyperaemia

Category	PT
Gastrointestinal	Gastrointestinal mucosal exfoliation
Gastrointestinal	Haemorrhagic erosive gastritis
Gastrointestinal	Intestinal angioedema
Gastrointestinal	Oesophageal mucosa erythema
Gastrointestinal	Oesophagitis
Gastrointestinal	Reactive gastropathy
Gastrointestinal	Reflux gastritis
Gastrointestinal	Remnant gastritis
Gastrointestinal	Ulcerative gastritis
Gastrointestinal	Abdominal discomfort
Gastrointestinal	Abdominal distension
Gastrointestinal	Abdominal pain
Gastrointestinal	Abdominal pain lower

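### The ectopic-mineralization event list counts tendon, ligament, articular and bursa calcification but has no enthesopathy term, so whether the same lesion is counted depends on how it is reported and coded

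*SAP*

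**What the plan says.** SAP 8.6.1 lists ectopic mineralization among the events to monitor that get their own TEAE summary. SAP 5.7 notes that no standardised MedDRA query exists and gives the rule: "Ectopic calcification related AE is defined using a MedDRA search of" the word calcification. Appendix 5 repeats the rule ("Ectopic mineralization: based on a MedDRA search of" that word) and prints the preferred terms. Among them are "Tendon calcification" and "Ligament calcification", as well as *Articular calcification* and *Bursa calcification*. No enthesopathy term is printed.

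Protocol 5.1.1 describes the adult disease as follows: "The initial presenting complaint in adults may be enthesopathy (calcification of the tendons, ligaments, and joint capsules". Protocol 7.5.4 names enthesopathy again among the signs and symptoms of XLH ("joint abnormalities and joint pain; enthesopathy; and osteoarthritis").

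**The concern.** On the protocol's own description, enthesopathy is calcification of structures that the SAP list already covers. A report worded as tendon calcification enters the category. The same lesion reported and coded as enthesopathy does not. The deciding factor is then the investigator's choice of word and the coder's choice of term, not the finding.

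The category matters because mineralization is a recognised risk of the mechanism. Protocol 5.2.3 reports it among the major toxicological findings, and protocol 7.2 lists ectopic mineralization among the risks to be monitored. The SAP Amendment 1 summary says the event categories were revised to fit the product's identified or potential risks. An omission of this kind can leave the category count unchanged or make it too low; it cannot make it too high.

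Such reports are plausible. Sites complete an XLH-specific list of signs and conditions (protocol 7.5.3.2). Radiographs of the spine, hands, long bones and feet are read locally for new abnormalities (protocol 7.5.1.2.1). Worsening of a pre-existing condition is an AE (protocol 8.5.4).

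**Working it through.** The plan states no figure for this category, so there is none to reproduce. The check has two parts.

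**1. What the list contains** (count of the ectopic calcification terms in SAP Appendix 5)

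- Distinct preferred terms: 50.
- Terms containing *calcification*: 32. Terms without it: 50 − 32 = 18, for example *Nephrolithiasis*, *Heart valve stenosis* and *Chondrocalcinosis*.
- Musculoskeletal terms: 8, namely *Articular*, *Bursa*, *Ligament*, *Tendon* and *Intervertebral disc calcification*, *Calcification of muscle*, *Chondrocalcinosis* and *Chondrocalcinosis pyrophosphate*.
- Terms containing *enthes*: 0.

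Set against the three structures in protocol 5.1.1:

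| Structure | Nearest listed term |
|---|---|
| Tendons | *Tendon calcification* |
| Ligaments | *Ligament calcification* |
| Joint capsules | *Articular calcification* (near equivalent) |
| Enthesopathy itself | none |

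Two things follow. Musculoskeletal mineralization is within the scope of the list as printed. And the search word does not explain the gap, because 18 of the 50 terms were included without it.

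**2. Size**

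Inputs: n = 20 subjects (protocol 7.1 and 7.6.4, approximate). Let m be the number of subjects who have an event coded as enthesopathy and no event under any listed term. The documents give no value for m, so it is assumed.

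Undercount in category incidence = m/n = m/20. The second column is in percentage points. The third is the Clopper-Pearson 95% interval for m events in 20 subjects, which is the interval for the corrected count if the printed list found no events.

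| m (assumed) | m/20 | 95% interval for m/20 |
|---|---|---|
| 0 | 0 | 0% to 16.8% |
| 1 | 5 | 0.1% to 24.9% |
| 2 | 10 | 1.2% to 31.7% |
| 3 | 15 | 3.2% to 37.9% |

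A subject who already has an event under a listed term is counted either way and adds nothing to m.

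**The case against.** Five arguments limit the point, and each stands at least in part.

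- **The pathology is not excluded.** Tendon, ligament and articular calcification are listed. A reader might infer that new enthesopathy is always left out; in fact it is missed only when coded outside the listed terms.
- **The coding is not known.** The documents do not say where verbatim enthesopathy goes in MedDRA 18.1. If it maps to a listed term, the gap closes.
- **The event is not lost from safety reporting.** SAP 8.6.1 tabulates all TEAEs by system organ class and preferred term, by relationship and by severity, and with about 20 subjects such a row would be visible. However, that row is not labelled as mineralization, and category incidence by subject cannot be rebuilt from preferred-term rows when a subject may have several. SAP 8.8.2.2 also covers other disease-related skeletal abnormalities on radiographs, but as an efficacy endpoint that does not name enthesopathy.
- **The purpose is inferred.** A reader might conclude that the category was meant to detect enthesopathy. No section says so. Protocol 7.3.3.1 monitors ectopic mineralization by renal ultrasound and ECHO, and the protocol presents enthesopathy as a feature of the disease. The eight musculoskeletal terms show that such lesions fall within the list, not that enthesopathy was a stated target.
- **The favourable statement in the protocol does not rest on this count.** Protocol 5.3 concludes that the drug's profile is "without evidence of increased ectopic mineralization or other concerns associated with the excess of FGF23". A reader might take that as a claim this list was built to support. But it concerns evidence to date, an earlier paragraph of the same section limits the reassurance to cardiac or renal mineralization, and the section was updated in 2017, after the SAP amendment of April 2016.

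A further objection is that adding a common disease feature would make the category less specific to the product in a study without a control group. That is a fair cost, and separate sub-rows answer it.

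**Conclusion.** The point holds in a limited form. As printed, the list captures the lesion described in protocol 5.1.1 when it is coded as tendon, ligament or articular calcification, and misses it when it is coded as enthesopathy. The size is 5 percentage points of category incidence for each subject missed, and zero if there are none. This rests on two assumptions: about 20 treated subjects, and a MedDRA 18.1 coding of enthesopathy that falls outside the 50 listed terms.

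The rows for one, two or three subjects are illustrations. A reader might take 10% or 15% against a reported 0% as true against planned incidence. The documents do not support that: it would need two or three subjects with reported events, all coded off the list, and no listed event in any subject. A bias toward no signal is possible but not shown. The change is still worth making, because it is cheap and the omission can act only toward a lower count.

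**What to change.** Look up the preferred term or terms to which enthesopathy codes in MedDRA 18.1. If they are not already listed, add them to the ectopic calcification list in Appendix 5 and to the definition in SAP 5.7. Report the category in three rows:

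- (a) all terms other than musculoskeletal, including renal, cardiac and vascular;
- (b) musculoskeletal terms, including enthesopathy;
- the total.

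Stable baseline enthesopathy stays out under the existing rules: SAP 8.6.1 summarizes only events with onset on or after the start of dosing, and protocol 8.5.4 defines an AE as a new or worsening condition.

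The cost is the added term or terms and the sub-rows, with no new data. The downside is that the total may rise because enthesopathy is a feature of XLH, and without a control group that rise cannot be attributed to the drug or to the disease. Row (a) keeps the renal, cardiac and vascular figure separate.

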## Appendix 6: Schedule of Events

VISIT TYPE / NUMBER	Ser  1	BL  2	HH  3	4	HH  5	6	HH  7	8	HH  9	HH  10	11	HH  12	HH  13	HH  14	15	HH  16	HH  17
WEEK	D-1	0	2	4	6	8	10	12	16	20	24	26	28	32	36	38	40
Informed Consent	X																
Inclusion/Exclusion Criteria	X																
Medical History & Demographics 	X																
Renal Ultrasound	X											X					
Chemistry  , Hematology  , Urinalysis	X								X			X			X		
2-hr and 24-hr Urine	X							X			X				X		
Urine Pregnancy Test 	X	X		X		X		X	X	X	X		X	X	X		X
Vital Signs 		X	X	X	X	X	X	X	X	X	X	X	X	X	X	X	X
Height		X									X				X		
Physical Examination		X						X			X				X		
PHEX mutation analysis		X															
Anti-KRN23 antibody (HAHA) 		X		X				X			X				X		
Serum Phosphorus	X	X	X	X 	X	X 	X	X 			X	X	X		X	X	X
Serum Calcium	X	X	X	X	X	X	X	X			X	X	X		X	X	X
Serum Creatinine	X							X			X				X		
Serum iPTH		X						X			X				X		
Serum FGF23		X		X		X		X			X		X		X		X

VISIT TYPE / NUMBER	Ser  1	BL  2	HH  3	4	HH  5	6	HH  7	8	HH  9	HH  10	11	HH  12	HH  13	HH  14	15	HH  16	HH  17
WEEK 	D-1	0	2	4	6	8	10	12	16	20	24	26	28	32	36	38	40
Serum 1,25(OH) 2 D		X						X			X				X		
Bone Biomarkers 		X										X					
ECHO, ECG		X										X					
WOMAC, BPI, SF36 		X							X			X				X	
6MWT, 3MSCT, TUG		X										X				X	
X-Ray 		X							X			X				X	
Interval History									X			X				X	
Prior and Concomitant Medications	X	X	X	X	X	X	X	X	X	X	X	X	X	X	X	X	X
Adverse Events	X	X	X	X	X	X	X	X	X	X	X	X	X	X	X	X	X
Weight		X		X		X		X			X				X		
Drug Administration		X		X		X		X	X	X	X		X	X	X		X

VISIT TYPE / NUMBER	HH  18	19	HH  20	HH  21	HH  22	HH  23	HH  24	HH  25	26
WEEK	44	48	50	52	56	60	64	68	72/ EoT
Informed Consent									
Inclusion/Exclusion Criteria									
Medical History & Demographics 									
Renal Ultrasound		X							X
Chemistry  , Hematology  , Urinalysis		X							X
2-hr and 24-hr Urine		X							X
Urine Pregnancy Test 	X	X		X	X	X	X	X	X
Vital Signs 	X	X	X	X	X	X	X	X	X
Height		X							X
Physical Examination		X							X
PHEX mutation analysis									
Anti-KRN23 antibody (HAHA) 		X							X
Serum Phosphorus 		X	X	X		X			X
Serum Calcium		X	X	X		X			X
Serum Creatinine		X							X
Serum iPTH		X							X
Serum FGF23		X							X
Serum 1,25(OH) 2 D		X							X
Bone Biomarkers 		X							X
ECHO, ECG		X							X

VISIT TYPE / NUMBER	HH  18	19	HH  20	HH  21	HH  22	HH  23	HH  24	HH  25	26
WEEK 	44	48	50	52	56	60	64	68	72/ EoT 
WOMAC, BPI, SF36 		X							X
6MWT, 3MSCT, TUG		X							X
X-Ray 		X							X
Interval History		X							X
Prior and Concomitant Medications	X	X		X	X	X	X	X	X
Adverse Events	X	X		X	X	X	X	X	X
Weight		X							X
Drug Administration	X	X		X	X	X	X	X	

1,25(OH)2D = 1,25-dihydroxy vitamin D; 3MSCT = stair climb test; 6MWT = 6-minute walk test; BL = Baseline; ECG = electrocardiogram; ECHO = echocardiogram; EoT = end of treatment; FGF23 = fibroblast growth factor 23; HAHA = Human Anti-Human Antibody (immunogenicity testing assay); HH = home health; HIV = human immunodeficiency virus; hr = hour; iPTH = intact parathyroid hormone; PHEX = phosphate regulating gene with homology to endopeptidases located on the X chromosome; Scr = Screening; TmP/GFR = the ratio of phosphorus tubule maximum (TmP) to glomerular filtration rate (GFR), or tubular resorption of phosphate; TUG = timed up and go (test)

 Screening tests may be spread out over Screening and Baseline assessments, but have to be performed before drug administration. Screening and Baseline visits may be conducted on consecutive days but may be conducted up to 7 days apart.

 Baseline Visit tests and assessments may be spread out over 2 consecutive days to accommodate considerable number of assessments.

 Home Health (HH) visits may also be conducted at the clinic depending on proximity of the subjects to the investigational site and local availability of home health resources.

 The visit window for visits 3 through 25 is ± 3 days. The visit window for the EoT visit at Week 72 is ± 5 days.

 Medical history to include review of previous test results for HIV antibody, hepatitis B surface antigen, and/or hepatitis C antibody. Viral testing will not be repeated in this study.

 This comprehensive metabolic profile will include the standard Chem-20 serum panel: Na, K, Cl, bicarbonate, blood urea nitrogen (BUN), creatinine and creatinine clearance, glucose, alkaline phosphatase, alanine aminotransferase [ALT], aspartate aminotransferase [AST]), gamma-glutamyl transferase (GGT), lactate dehydrogenase, phosphorus, uric acid, calcium, total protein, albumin, cholesterol and triglycerides, total bilirubin, and indirect bilirubin.

 Complete blood count, differential, and platelet count.

 For women of childbearing potential only. A serum pregnancy test will be performed in the event of a positive or equivocal urine pregnancy result.

 Vital sign measurements consist of seated systolic/diastolic BP measured in millimeters of mercury (mm Hg), HR (beats per min), respiration rate (breaths per min), and temperature in degrees Celsius (°C). Obtain at the beginning of each visit before any additional assessments are completed.

 If the development of anti-KRN23 antibodies is suspected in a given subject, samples may be obtained at additional time points on a case-by-case basis, if warranted.

 Two serum samples should be collected at clinic visits for serum phosphorus measurements. One sample will be read locally for determination of dosing decision; the other will be sent for analysis by the central laboratory.

 Bone biomarkers will include serum measures of total serum ALP, bone-specific ALP (BALP), CTx, and P1NP.

 Western Ontario and McMaster Universities Osteoarthritis Index (WOMAC), Brief Pain Inventory (BPI), and SF-36 self-reported patient-reported outcomes (PROs) tools.

 Standard radiographs will be customized by patient and will be repeated every 3 months or until specified lesions are healed.

 Those subjects who terminate the study early will be asked to come back to the clinic for a final assessment. Every reasonable effort should be made to have subjects return to the clinic for the final assessment; however, subjects who are unable to return to the clinic for the final assessment will be given the option of providing blood and urine samples as part of a HH visit.
